8.8 Other Elements of Analysis Plan

8.8.1Analysis Sets

The following analysis sets are defined:

Intent-to-treat (ITT): The ITT analysis set will include all randomized patients.

Modified Intent-to-treat (mITT): The mITT analysis set will include all patients with any exposure to a study treatment (active or placebo), where patients will be classified by the group in which they are randomized, regardless of the treatment received; and who have at least one WOMAC assessment subsequent to randomization. Primary, secondary, and exploratory effectiveness analyses will be conducted in the mITT analysis set. It is necessary to only include patients with at least one post randomization WOMAC assessment for use in the MMRM. Baseline carried forward is likely to produce substantial bias in estimated treatment differences. It is reasonable to expect that baseline carried forward bias is substantial and perhaps even larger than might be expected from excluding a very small number of patients with no follow-up subsequent to randomization. For this reason, baseline carried forward will not be conducted. It is acknowledged that if there are more than a very small percentage of patients with no follow-up subsequent to randomization, results from this clinical trial may not be adequately interpretable to provide sufficient evidence of effectiveness depending upon the robustness of primary analyses and the consistency of supporting analyses.

As Treated (AT): The AT analysis set will include all patients randomized with any exposure to a study treatment (active or placebo), where patients will be classified by the treatment actually received. Safety analyses will be performed in the AT analysis set. If there are no patients receiving the incorrect treatment, then this analysis set will be identical to mITT.

Per protocol (PP): The PP analysis set will include subjects with no major protocol deviations. In particular, the PP analysis will exclude patients that start but do not complete all injections associated with a study treatment. The PP analysis set will also exclude patients with major violations of inclusion or exclusion criteria or who receive confounding concomitant medication expected to significantly impact the primary outcome measure. Secondary effectiveness analyses will be performed using the PP analysis set.

The primary and conditional hypotheses will also be tested using the ITT analysis set and in an analysis set restricted to complete cases using the same MMRM. Comparison among results from these three analyses will provide FDA the capability of determining robustness of conclusions relative to assumptions regarding missing data. In the case of no missing data, these three analyses are identical. Therefore, it will be a study goal to minimize the number of patients with early termination and missing data for other reasons as the most important way of addressing this issue.

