8.3 Statistical Methods for Testing Superiority

8.3.1 MMRM

Superiority testing will be performed using a mixed model for repeated measures (MMRM) analysis of covariance (ANCOVA) Model.³⁹ The MMRM approach is a direct likelihood approach requiring specialized statistical software. For this study, all MMRM parameters will be estimated using SAS PROC MIXED. The MMRM model is notable for its inclusion of all available data from all eligible subjects and does not require their exclusion as in complete case analysis or arbitrary assignment of some value as in Last Observation Carried Forward (LOCF). Inclusion of outcome data from time points earlier than Months 6 informs the implicit imputation of missing Month 6 values through the covariance matric used to model the random effects.

The random effects in the MMRM model will based on the so-called 'unstructured covariance matrix' in which variances over time are allowed to vary as are the pair-wise correlations over time.

The values over time will include all WOMAC scores, namely at each of the 3 follow-up time points, visit 5 / 2 months, visit 6 / 3 months, and visit 7 / 6 months.

All WOMAC values will be included in the analysis even if they are obtained outof-window. However, the fraction of out-of-window visits will be summarized at each time point.

The contrast indicated by the primary hypotheses above, $\delta(pain)_{ACP} - \delta(pain)_{Control}$ will be estimated as the treatment group contrast from baseline to Month 6 in the WOMAC score derived from the MMRM. The null hypothesis is that the true value of this contrast is equal to zero. The same approach will be taken for the WOMAC Function score if superiority in pain relief is demonstrated.

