8.3.3 Details Concerning the MMRM

As stated above, the covariance matrix for MMRM is an unstructured covariance matrix in which each of the 3 variances (2 months, 3 months, and 6 months) are free to vary as are the 6 pairwise covariances. That is, the covariance matrix for the MMRM will not inlcude any random effects per se, but accounts for correlations among errors by specifying the form of the covariance matrix. The MMRM employs an unstructured covariance in order to produce inferences that are valid under the so-called 'missing at random' (MAR) assumption which is more generally true than the 'missing completely at random' assumption that is required for validity of analyses restricted to complete cases.

The longitudinal model will be specified as a repeated measures model that expresses the WOMAC score as a linear function of treatment, time, treatment-by-time interaction, and a covariate of the baseline pain measurement.

The model can be mathematically expressed as:

 $Y_i = X_i\beta + e_i$

- Yi is change from baseline to Month 6 in WOMAC Pain or Function scores
- βis a vector of fixed-effect regression parameters which includes:
 - $\circ \mu$, the overall mean
 - \circ θ , the treatment effect
 - \circ τ , a vector of post-baseline time effects
 - \circ **η**, a vector of treatment-by-time interaction effects,
 - $\circ \phi$, a vector of covariate effect parameters that only includes baseline WOMAC score but in general could include additional baseline variable,
- X is a design matrix for the fixed effects, and
- **e** is the error vector with
 - $\circ \quad \mathbf{E}(\mathbf{e}) = \mathbf{0} \text{ and}$

• $Var(e) = \sigma_e^2 V_{unstructured}$.

The specific model to be used may be expressed as:

$$Y = b_{int} + b_{base} + b_T + b_{2M} + b_{3M} + b_{6M} + b_T b_{2M} + b_T b_{3M} + b_T b_{6M}$$

With parameters as explained below.

Parameter	Represents
Y	Change from baseline
b _{int}	Model intercept
b _{base}	Baseline value
b_T	Indicator for Active Treatment
$b_{2M} b_{3M}, b_{6M}$	Indicator for each visit
bтb2м, bтb3м, bтb6м	Indicators allowing varying treatment differences at each visit

From this model estimates of treatment effect at specific visits and specifically at Month 6 difference may be obtained as follows.

 $T_{M6} = b_{int} + b_{base} + b_T + b_T b_{M6}$

 $S_{M6} = b_{int} + b_{base}$

 $\Delta_{M6} = T_{M6} - S_{M6} = b_T + b_T b_{M6}$

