Where e.g. T_{M6} and S_{M6} are the expected changes from baseline to Month 6 in the WOMAC scores in the active and sham control groups, respectively, in terms of these model parameters, the superiority hypotheses are:

H₀: $\Delta_{M6} = 0$ H₁: $\Delta_{M6} > 0$ when larger values reflect improvement or

H₀: $\Delta_{M6} = 0$ H₁: $\Delta_{M6} < 0$ when smaller values reflect improvement

The following SAS Proc Mixed statements provides the test for this null hypothisis. The key results is listed among the results provided by the 'slice' option of the LSMEANS statement. One of these will provide the treatment group contrast at Month 6.

proc mixed data=dataset method=ml;

class patid trt time;

model womac_pain = trt time trt*time womac_pain_bl / s chisq;

repeated time / type=un subject=patid; lsmeans trt*time / slice=time; run;

The Month 6 treatment group contrast, the p-value associated with the null hypotheses and 95% two-sided confidence interval will be derived from the MMRM in order to test the superiority hypotheses for the primary endpoint and co-primary endpoints.

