in mean percentage changes so large is likely clinically significant given the known reliability and validity of the WOMAC Pain score.

Randomization will be 2:1 in order to increase precision when characterizing the safety profile of the investigational treatment. We assume a one-sided type 1 error of α =0.025 and a standardized mean difference of 0.80 and determined that a total sample size of N=78 (52 ACP and 26 control) patients are required for 90% power. **This value is increased by 15% to N=90 (60 ACP and 30 control)** to account for potential loss-to-follow-up or other exclusions from the primary effectiveness analysis set.

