8.8.6 Treatment of Missing Data

All patients contributing at least one follow-up WOMAC Total score will be included in the primary superiority test through the use of the mixed model for repeated measures (MMRM) in the mITT analysis set. In this way patients with incomplete follow-up are retained and contribute to the primary superiority test.

As noted elsewhere, FDA has previously recommended to not include many baseline covariates in the MMRM due to the modest sample size. Therefore, the only baseline covariates available for implicit imputation of changes from baseline to Month 6 (180 days) is the baseline value itself and treatment group. It follows then, that for the ITT analysis, the MMRM will implicitly impute missing changes from baseline to Month 6

(180 days) for patients with no follow-up data as the within treatment group mean change score modified by the effect of the baseline value

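### Comparing the mITT, ITT and complete-case fits cannot show robustness to departures from missing at random, because ITT and mITT agree almost by construction and complete case rests on a stronger assumption

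*Combined protocol and SAP*

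**What the plan says.** Section 8.8.1 (Analysis Sets) makes mITT the primary effectiveness set: patients with any exposure to study treatment and at least one WOMAC after randomization. For ITT, "The ITT analysis set will include all randomized patients". The primary and conditional hypotheses are then retested with the same model in ITT and in complete cases, and the section concludes: "Comparison among results from these three analyses will provide FDA the capability of determining robustness of conclusions relative to assumptions regarding missing data".

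The model is a direct-likelihood MMRM. Its responses are the WOMAC scores "namely at each of the 3 follow-up time points, visit 5 / 2 months, visit 6 / 3 months", and visit 7 at 6 months (Section 8.3.1). Baseline enters as a covariate in the SAS code of Section 8.3.3: "model womac_pain = trt time trt*time womac_pain_bl / s chisq".

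Section 8.3.3 says the MMRM is valid under MAR. It names missing completely at random (MCAR) as the less generally true "assumption that is required for validity of analyses restricted to complete cases". Section 8.8.6 covers patients with no follow-up: "It follows then, that for the ITT analysis, the MMRM will implicitly impute missing changes from baseline to Month 6", using the arm's own mean change adjusted for baseline. Section 8.8.1 rejects baseline carried forward. It also accepts that the trial may be hard to interpret if more than a few patients have no follow-up, "depending upon the robustness of primary analyses and the consistency of supporting analyses".

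**The concern.** The sentence in 8.8.1 is general. It promises a reading on missing-data assumptions without limit, whereas the three fits cover a narrow part of that question. Two of them use the same likelihood contributions. The third assumes more than the primary analysis does.

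No planned analysis lets missing patients do worse than their arm and observed scores predict. There is no delta-adjusted, reference-based, pattern-mixture or tipping-point analysis, that is, none under missing not at random (MNAR). The per-protocol, added-covariate and site analyses answer other questions.

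What is at stake is interpretation. Section 8.8.1 rests interpretability partly on whether the supporting analyses are consistent. One of them is consistent almost by construction, so three concordant results could be presented as robustness that was never examined.

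**Working it through.** **Scale of missing data planned for.** Section 8.4.1 uses a standardized difference of 0.80, one-sided alpha 0.025 and 2:1 allocation. A noncentral-t calculation for 52 and 26 patients gives 90.8% power, so N = 78 for 90% power is reproduced. Then 78 × 1.15 = 89.7, rounded to 90, "to account for potential loss-to-follow-up or other exclusions from the primary effectiveness analysis set". That leaves room to lose 12 of 90 = 13.3%.

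**Why ITT and mITT coincide.** The observed-data log-likelihood is a sum over patients of the log density of each patient's observed Month 2, 3 and 6 scores, given arm, visit and baseline. A patient with none of these scores has an empty term. Keeping or removing that patient changes neither the estimate nor its SE. The implicit imputation in 8.8.6 correctly describes the MAR prediction, but it changes no result.

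- Check: maximum-likelihood fits of the 8.3.3 model to a simulated 60/30 trial with two such patients gave 2.1809 (SE 0.7430) for both ITT and mITT.
- Exception: mITT also requires exposure. When two patients with scores were treated as never injected and dropped from mITT, the estimate moved to 2.195. That reflects exposure, not missing data.

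**What complete case can and cannot show.** Average Month 6 ACP advantage over 600 simulated trials per row, about 13% missing, planned effect 0.80 × 3.4 = 2.72. The visit correlation (0.6), dropout patterns and shifts are assumptions, not document figures.

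| Mechanism | Full data | mITT = ITT | Complete case |
|---|---|---|---|
| MCAR | 2.69 | 2.71 | 2.71 |
| MAR, dropout depends on Month 3 | 2.74 | 2.73 | 2.98 |
| MNAR, missing ACP 2.72 worse | 2.40 | 2.73 | 2.73 |
| MNAR, missing ACP 7.7 worse | 1.74 | 2.76 | 2.74 |
| MNAR, dropout depends on Month 6 value | 2.74 | 2.95 | 3.13 |

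In rows 3 and 4 all three planned analyses agree and overstate the effect by about 0.3 and 1.0 points. In row 5 a gap appears, but it does not reveal how far mITT is off. In row 2 a gap of similar size appears although mITT is unbiased.

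**Consequence for the test at 13.3% missing.** SD 3.4 comes from Section 8.4.1. The SE is held fixed.

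- SE = 3.4 × √(1/52 + 1/26) = 0.817. Threshold = t(0.975, 76) × SE = 1.992 × 0.817 = 1.63.
- ACP-only tipping delta = (estimate − 1.63)/0.1333. This gives 8.2 points at 2.72, 2.8 at 2.0 and 1.3 at 1.8.
- If missing patients in both arms are control-like, the MAR estimate is diluted by the factor (1 − 0.1333). MAR estimates from 1.63 to 1.63/0.8667 = 1.88 would lose significance.
- Chance of landing there if the MAR estimate centres at 2.72: Φ(−1.03) − Φ(−1.34) = 0.151 − 0.090, about 6%.
- Chance if 2.72 is instead the effect in all randomized patients: the MAR estimate centres at 2.72/0.8667 = 3.14, and Φ(−1.54) − Φ(−1.85) = 0.061 − 0.032, about 3%.

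**The case against.** **The consequence is small at planned effects.** This stands. With the pilot control mean of 9.1 at Month 6, an effect of 2.72 puts the ACP mean near 6.4. A delta of 8.2 would put missing ACP patients near 14.6, well above the pilot ACP baseline of 10.2. At an estimate of 4.2 the delta is (4.2 − 1.63)/0.1333 = 19.3 on a 0 to 20 scale. Only results near the threshold are fragile.

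**The plan never claims to examine departures from MAR.** It speaks of missing-data assumptions in general, and mITT against complete case does bear on one of them, as 8.3.3 explains. So the sentence is too broad rather than wholly wrong. Nothing in it limits the claim to MAR versus MCAR, though.

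**Complete case can react to MNAR dropout.** It can, as row 5 shows, so a reader should not infer that the comparison is worthless or speaks to MCAR alone. It still does not bound the bias of the MAR analysis.

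**Missing data are already addressed.** Section 8.8.1 gives reasons against baseline carried forward, admits the limit on interpretability and puts prevention first. All of this is sound, but none of it assesses the data that remain missing.

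A reader might also infer that the primary MMRM is invalid or its result biased. The documents do not support that. MAR is a defensible primary assumption, and nothing here shows that it fails.

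**Conclusion.** The point holds. The three-way comparison does not have the property that 8.8.1 gives it. ITT/mITT agreement carries no information about missing data. This follows from the model and needs no assumption about dropout or correlation. The only exception is a never-injected patient with a Month 2, 3 or 6 score. The complete-case comparison can warn that missingness is not completely random, but it neither shows nor bounds bias under MNAR, and agreement is no evidence for MAR.

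The primary test is unchanged. The practical risk is confined mainly to a result near the threshold: about 3% or 6% at 13.3% missing, depending on which effect is taken to be 2.72. Those percentages and the tipping deltas rest on SD 3.4, a fixed SE and, for the percentages, control-like missing patients with equal missing shares in both arms. The plan should be corrected because it would present forced agreement as robustness and the remedy is cheap.

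**What to change.** Keep the mITT MMRM as primary; the ITT run may stay.

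1. Reword the sentence in 8.8.1. State that ITT/mITT agreement is not evidence about missing data. State that mITT against complete case checks sensitivity to MAR versus MCAR and does not bound departures from MAR.
2. Add to 8.8.1 one pre-specified MNAR sensitivity analysis in all randomized patients. Either of these would serve:
   - control-based multiple imputation of missing ACP Month 6 scores; or
   - a delta-adjusted tipping point, with a plausible delta range stated in advance (for example, up to the shift that makes missing ACP patients control-like or returns them to baseline) and a rule for imputed pain scores outside 0 to 20.
3. Report by arm how many randomized patients have no Month 2, 3 or 6 score. This count includes mITT patients whose only follow-up WOMAC is at Week 1 or 2, since those visits are not in the model.

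The cost is SAP wording and some programming before unblinding. No new data or patients are needed, and the primary test and analysis sets do not change. The drawback is a supporting estimate that may be less favourable than the primary one.

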8.8.2 Randomization and Blinding

A site stratified, randomized block randomization will be performed such that within each block, patients will be allocated to either ACP or control in a 2:1 randomization ratio Patients, physicians, and study personnel will be blinded to treated until end of the study to prevent bias in estimated treated differences.

8.8.3 Description of baseline characteristics

Demographic and baseline characteristics will be tabulated and compared between the investigational group and control group. Variables to be compared will include baseline knee assessment, disease severity, age, gender, Body Mass Index (BMI), weight and height, race and ethnicity, disease histories, and concomitant medications and therapies. Descriptive p-values will be determined using Wilcoxon rank sum tests for continuous measures and chi-square or exact tests for categorical variables. However, focus will be on clinical significance of group differences and only secondarily on p-values, since these p-values are not associated with planned comparison. If there are clinically significant group differences for any baseline variable, then supporting analyses will include adding these covariates to the MMRM used in primary superiority testing and evaluating the impact of the imbalance on primary findings.

8.8.4 Description of Effectiveness Outcome

WOMAC Pain, Function, Stiffness, and Total scores and the as well as change scores will be summarized at each planned follow-up visit [Pre-Op, 1 Week, 2 Weeks, 2 Months (60 days), 3 Months (90 days), 6 Months (180 days), and 12 Months (365 days)] using means, standard deviations, medians, minimum, and maximum values. Standardized effect sizes (mean difference divided by the standard deviation of differences) will be computed at each time point for each continuous measure in order to facilitate assessment of group differences across measures as well as time. Pooled t-tests and Wilcoxon rank sum tests will be provided as additional descriptive measures. There will be no imputation of missing values for secondary endpoint and exploratory endpoints and no control for type I error in the set of exploratory endpoints. Graphical displays of selected endpoints will be provided to provide visual assessments of group differences over time.

8.8.5 Site Poolability

A random effects model for site to site heterogeneity among treatment group differences in mean improvement in WOMAC Pain score will be evaluated. If important heterogeneity is observed, further analyses will be performed aimed at determining the source of this heterogeneity and its impact on estimates of treatment group differences.

8.8.6 Treatment of Missing Data

All patients contributing at least one follow-up WOMAC Total score will be included in the primary superiority test through the use of the mixed model for repeated measures (MMRM) in the mITT analysis set. In this way patients with incomplete follow-up are retained and contribute to the primary superiority test.

As noted elsewhere, FDA has previously recommended to not include many baseline covariates in the MMRM due to the modest sample size. Therefore, the only baseline covariates available for implicit imputation of changes from baseline to Month 6 (180 days) is the baseline value itself and treatment group. It follows then, that for the ITT analysis, the MMRM will implicitly impute missing changes from baseline to Month 6

(180 days) for patients with no follow-up data as the within treatment group mean change score modified by the effect of the baseline value

8.7 Subgroup Analyses

Primary and selected secondary effectiveness analyses and selected adverse event comparisons will be stratified according to site subject demographics and baseline characteristics.

8.8 Safety Analysis

Assessment of safety will be based primarily on the incidence and severity of complications and adverse reactions associated with the treatment. Adverse event rates will be summarized by type of AE and for specific AEs in two ways: 1) per patient using counts and percentages and 2) by event, summarizing event counts by visit interval over time. Treatment and procedure related events will be summarized by severity. Events listings will be provided that include details such as relatedness, severity, onset and resolution status will be provide for all events and for relevant subsets of events such as serious events and related events. All safety endpoints will be summarized separately for investigational and control groups. Incidence rates for grouped and individual adverse events will be compared using counts, percentages, and descriptive Fisher's exact test nominal p-values. Grouped adverse events will include events at least possibly related to study treatment and serious adverse events.

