3.2.5 Safety Endpoint

Adverse events will be compared between ACP treatment and the control in terms of both per patient incidence and total.

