8.7 Safety Endpoints

The primary safety endpoints for this study are based on adverse events. Details regarding analyses of adverse events are provided below. Briefly, adverse event endpoints will include, but are not limited to, the following patient specific endpoints:

- Any adverse event (per patient)
- Any treatment related AE
- Any serious AE
- Any serious AE that is treatment related
- Patient death

Specific endpoints such discomfort and pain, erythema, swelling, bruising, hemorrhage, and papules will be compared between treatment groups in terms of both per patient incidence rates and total counts. Fisher's exacts tests will be used to provide descriptive comparisons between incidence rates. Counts of AEs will be displayed overall and over time.

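### Adverse event incidence is compared between arms by counts, percentages and Fisher p-values with no confidence interval; adding one is a cheap improvement that shows what size of excess the data exclude.

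*Combined protocol and SAP*

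**What the plan says.** 8.7 Safety Endpoints states: "The primary safety endpoints for this study are based on adverse events". It lists five per-patient endpoints (any event, any treatment-related event, any serious event, any serious treatment-related event, death) and six specific reactions or reaction groups, such as swelling and bruising. Section 3.2.5 gives the aim: "Adverse events will be compared between ACP treatment and the control in terms of both per patient incidence and total".

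The between-arm method for incidence appears twice and is the same both times. 8.7 Safety Endpoints says: "Fisher's exacts tests will be used to provide descriptive comparisons between incidence rates". 8.8 Safety Analysis says: "Incidence rates for grouped and individual adverse events will be compared using counts, percentages, and descriptive Fisher's exact test nominal p-values". Total event counts are tabulated and listed without a test.

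The only interval planned for the trial's results concerns effectiveness. Section 8.3.3 says: "The Month 6 treatment group contrast, the p-value associated with the null hypotheses and 95% two-sided confidence interval will be derived from the MMRM".

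On allocation, 8.4.1 says: "Randomization will be 2:1 in order to increase precision when characterizing the safety profile of the investigational treatment". The documents give no expected adverse event rate, no power or precision statement for safety, and no safety margin.

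**The concern.** The effectiveness contrast will be reported with an estimate, a p-value and an interval. The adverse event comparison will have counts and percentages by arm and a p-value. In a trial of 90 patients the useful safety question is what size of excess the data are compatible with, and a p-value does not answer it. A Fisher p-value near 1 can arise when a sizeable excess is still compatible with the counts, and the planned tables would not show that.

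The plan also chose unequal allocation to gain precision on ACP safety, but names no measure that would report that precision. At stake is how informative the safety tables are, not the validity of a planned test or claim.

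**Working it through.** **Inputs.** Arm sizes of 60 ACP and 30 control come from 8.4.1. Event rates are assumptions, because the documents state none. Two-sided 0.05 is also an assumption, because the plan sets no safety significance level.

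**The plan's own figure.** 8.4.1 gives no safety calculation, only the effectiveness one: effect size 0.80, one-sided 0.025, 2:1, 90% power, N = 78. With the noncentral t distribution, 50 + 25 gives 89.7% power and 52 + 26 gives 90.8%, so 78 is reproduced. Then 78 × 1.15 = 89.7, rounded to 90. The arm sizes therefore follow from effectiveness alone.

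**Power of the Fisher test.** Power is the sum, over all 61 × 31 possible tables, of Bin(a; 60, pA) × Bin(b; 30, pC) for those tables with two-sided Fisher p ≤ 0.05.

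| Control rate | ACP rate | Power at 60 v 30 |
|---|---|---|
| 5% | 15% | 19% |
| 10% | 20% | 16% |
| 10% | 25% | 35% |
| 20% | 40% | 43% |
| 0% | 10% | 25% |
| 10% | 40% | 87% |

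Moderate excesses are usually missed; a very large one is usually detected. At 52 v 26, power is 12% for 10% v 20% and 41% for 20% v 40%.

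**What an interval adds.** The Newcombe interval uses Wilson limits (l, u) for each arm:
- lower limit = d − √[(pA − lA)² + (uC − pC)²]
- upper limit = d + √[(uA − pA)² + (pC − lC)²]

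For 6/60 v 3/30, d = 0. The Wilson limits are 4.66% to 20.15% for ACP and 3.46% to 25.62% for control.
- Lower: −√(5.34² + 15.62²) = −16.5 points
- Upper: +√(10.15² + 6.54²) = +12.1 points

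Fisher gives p = 1.0 for the same table. Other tables:

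| ACP | Control | Fisher p | Difference (points) | 95% Newcombe interval |
|---|---|---|---|---|
| 12/60 | 3/30 | 0.37 | +10.0 | −7.6 to +23.5 |
| 6/60 | 0/30 | 0.17 | +10.0 | −2.5 to +20.1 |
| 7/60 | 0/30 | 0.09 | +11.7 | −1.1 to +22.2 |

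**What 2:1 gives the ACP arm.** With zero events the Clopper-Pearson upper 97.5% limit is 1 − 0.025^(1/n): 6.0% at n = 60 and 7.9% at n = 45. At a 10% rate the standard error √(0.1 × 0.9/n) is 3.9 points at n = 60 and 4.5 at n = 45. The Fisher comparison loses slightly from 2:1: for 10% v 20%, power is 0.159 at 60/30 and 0.179 at 45/45.

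**The case against.** The strongest reply is that the plan does not use these p-values to decide anything. They are labelled descriptive and nominal, there is no safety hypothesis or threshold, and study success rests on WOMAC Pain alone. A reader might infer that the plan will treat a non-significant Fisher result as evidence of comparable safety. No section says so, and the power figures above describe a 0.05 rule that the plan does not set.

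A reader might also infer that clear harm would be hidden. The tables do not show that. For 7/60 v 0/30 the interval includes zero, so interval and p-value agree that an excess is not established; the interval only adds the bound. The percentages by arm, severity summaries and listings in 8.8 and 8.9.1 would still display such a contrast, and power is high for a very large excess.

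A third inference would be that the benefit of 2:1 is lost unless an interval is printed. It is not: the reported ACP percentage is itself more precise with 60 patients than with 45. Without an interval, that precision is simply not stated.

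It is also true that a reader could compute intervals from the published counts, and that unadjusted intervals on at least 5 + 6 = 11 endpoints, with no margin to judge them against, need careful reading. These points all stand. They reduce the matter to one of reporting, but do not supply the missing bound or commit the sponsor to giving it.

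**Conclusion.** A cheap improvement, not an error that invalidates any planned conclusion. That no interval is planned for a safety rate or difference is a plain reading of the text. The size of the gap depends on assumed event rates. For uncommon to moderately common events at 60 v 30, Fisher power for a doubling of risk is 16% (from 10%) to 43% (from 20%), and the upper limit for the excess in the worked tables is between 12 and 24 points. A p-value conveys none of this. An interval describes the same data better and reports the precision that 8.4.1 gives as the reason for the allocation ratio.

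**What to change.** In 8.7 Safety Endpoints and 8.8 Safety Analysis, state that for each per-patient safety endpoint (the five listed, and each specific reaction) the tables will give:
- the risk difference, ACP minus control, with a 95% Newcombe or exact unconditional interval, naming which one in advance;
- the ACP-arm rate with a 95% Clopper-Pearson interval, including when no events occur (upper limit 6.0% for 0/60).

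The Fisher p-values may stay, labelled descriptive as now. State that the intervals are unadjusted for multiplicity and descriptive.

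The cost is a few lines of text and an extra column in the adverse event tables; no new data or patients are needed, and the primary test is untouched. The downside is that the intervals will be wide and will show openly that excesses of roughly 12 to 20 points or more often cannot be ruled out.
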